13.1.4. Key Secondary Efficacy Analyses

The key secondary efficacy endpoints will compare OCA to placebo on the following:

- Time to first occurrence of MELD score ≥ 15
- Time to liver transplant or death (all-cause)
- Change from Baseline in total bilirubin at end of study
- Change from Baseline in ALP at end of study

The key secondary efficacy analyses will compare randomized OCA to randomized placebo in ITT population with respect to the key secondary efficacy endpoints. Only adjudicated events will be included in time-to-event analyses. The comparison (hypothesis testing) will be conducted as specified in [Section 13.1.10](#) in a sequential closed testing gate-keeping procedure, provided that the primary efficacy endpoint comparison is statistically significant in favor of the OCA treatment group. If the primary comparison is not statistically significant then comparison of the secondary endpoints will be considered as descriptive and exploratory. This procedure controls the study-wise type I error.

The 2 treatment groups will be compared using the same methodology as specified for the primary efficacy analysis ([Section 13.1.3](#)).

Analyses of change from Baseline to end of study in ALP and total bilirubin will be compared between treatment groups using analysis of covariance (ANCOVA) with change from Baseline as the dependent variable including treatment group and randomization stratification factor as

fixed effects and the Baseline values as a covariate. The same analysis will be carried out using percentage change from Baseline as the dependent variable.

Descriptive statistics of the laboratory values will be summarized by treatment group. The results, change from Baseline, and percentage change from Baseline values as well as estimates of least-square means, standard errors, and 95% CIs will be presented by treatment group. Estimates of the mean difference between treatment groups, the standard error of the difference, and 95% CI of the difference will be presented.

13.1.5. Additional Secondary Efficacy Analyses

The following time to event secondary efficacy analyses will compare randomized OCA versus randomized placebo using the ITT population:

- Time to each component of the primary efficacy endpoint (except MELD score ≥ 15 which is captured above)
- Time to development of varix/varices
- Time to liver-related death
- Time to liver-related death or liver transplant
- Time to liver-related death, liver transplant, or MELD score ≥ 15

The same analysis methodology as used for the primary efficacy analysis will be used for these secondary efficacy analyses. Similar endpoints, where available, will be analyzed to compare OCA to historical controls as described below in [Section 13.1.8](#).

Analyses of changes in liver biochemistry (GGT, ALT, AST, conjugated bilirubin, albumin, and INR) will be summarized and analyzed using the same methodology as specified in [Section 13.1.4](#) for the key secondary analyses of change in ALP and total bilirubin.

Progression to cirrhosis will be assessed in the subset of subjects considered non-cirrhotic at baseline using available medical history, clinical, and laboratory assessments as well as baseline TE, where available. Specifically, subjects with no clinical, laboratory, or radiological evidence of cirrhosis at baseline and/or a TE liver stiffness of < 16.9 kPa ([Corpechot 2012](#)) will be considered non-cirrhotic (See [Section 9.7.3.1](#)). Progression to cirrhosis will be assessed by the development of clinical, laboratory, or radiological evidence of cirrhosis and/or when liver stiffness increases to ≥ 16.9 kPa during the trial in which case histological progression to cirrhosis should be confirmed by biopsy unless not medically indicated. Using this definition for progression to cirrhosis, the percentage of non-cirrhotic subjects progressing to cirrhosis during the treatment period will be summarized by treatment group and compared using a Cochran–Mantel–Haenszel test stratified by the randomization stratification factor.

Analyses for the histological assessment conducted as part of the biopsy sub-study are defined in [Appendix C](#)).

Analyses of changes in MELD score, Child-Pugh score, Mayo Risk Score (MRS), IgM, CRP, TNF- α , FGF-19, CK-18, C4, and ELF score will be summarized and analyzed using the Wilcoxon Rank Sum Test to compare treatment groups. The median differences and 95% CI of the median differences between treatment groups will be constructed using Hodges-Lehmann

estimate. If the median differences between treatments are not symmetrical around the median, the Sign Test may be used.

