AE = adverse event; β -hCG = beta human chorionic gonadotropin; DEXA = dual-emission X-ray absorptiometry; EOS= End of Study; EOT = End of Treatment; FGF-19 = fibroblast growth factor-19; FIS = Fatigue Impact Scale; IP = Investigational Product; M = month, TE = transient elastography; VAS = Visual Analogue Scale; wk = week

- ^a In subjects following the standard dosing regimen, the post-titration visit must be performed only after the first up-titration to 10 mg OCA or matching placebo, or after ≥ 3 months at a decreased dose or frequency. Post-titration visits must be performed 1 month \pm 1 week after any up-titration in dose and/or frequency in subjects following modified dosing due to Child-Pugh B and Child-Pugh C hepatic impairment.
- ^b As soon as possible upon study discontinuation and as near as possible to last dose taken.
- ^c Visits should be based on Day 0 (not on the prior visit) with the exception of the Post-Titration Visit, which is based on the date of titration.
- ^d The yearly physical exam will include an assessment of smoking and alcohol consumption history and current habits for both.
- ^e Mayo Risk Score will be calculated based on central laboratory evaluations, diuretic use data, and peripheral edema assessment data captured in the CRF.
- ^f Child-Pugh Score will be calculated based on ascites assessment, hepatic encephalopathy grade, and central laboratory evaluations per the Child-Pugh scoring system noted in the case report form.
- ^g Height will be collected at this visit.
- ^h The EQ-5D-5L and FIS Quality of Life questionnaires are validated for use in multiple languages. If a validated translation is not available in the local language required for a specific study subject, the data from that questionnaire will not be collected (See [Section 11.1.2.2](#) and [Section 12.2.6](#)).
- ⁱ Transient elastography (TE) will be conducted at 6-month intervals at all study sites where the Fibroscan® TE device is available. Not required if done within 3 months of visit
- ^j DEXA will be conducted at 12-month intervals at all study sites where the DEXA device is available. Not required if done within 6 months of visit.
- ^k Endoscopy will be conducted at all study sites where the device is available to assess for the presence of oesophageal varix/varices.

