9.7.7. Day 0 Procedures (Randomization)

- Review inclusion and exclusion criteria for eligibility.
- Assess and record vital signs (weight, temperature, sitting heart rate, respiratory rate, and sitting blood pressure).
- Quality of Life and Subject questionnaires (see [Section 11.1.2.2](#) and [Section 12.2.6](#)).
- Perform transient elastography at all study sites with access to Fibroscan® TE device. If TE has been done within 3 months of Day 0 and a report/adequate data are available, a pretreatment TE at Day 0 is not required. If the TE cannot be performed on Day 0 (eg, device/technician unavailability, scheduling issues, TE data is needed to inform cirrhosis assessment, etc), the procedure may be completed within the screening visit window, at Screening Visit 1 (if data is needed for cirrhosis assessment) or as close as possible to the Day 0 visit, preferably, after subject eligibility has been confirmed.
- Conduct a DEXA bone density scan (at all study sites where device is available); document whether the subject stopped taking her/his calcium supplements for 48 hours before the scan and medications for osteoporosis or osteopenia on the day of the scan, if applicable. If DEXA has been done within 12 months of Day 0 and a report/adequate data are available, a pretreatment DEXA at Day 0 is not required. If the DEXA cannot be performed on Day 0 (eg, device/technician unavailability, scheduling issues, etc), the procedure may be completed within the screening visit window, as close as possible to the Day 0 visit, preferably, after subject eligibility has been confirmed.
- Perform an esophagogastroduodenoscopy (endoscopy; at study sites, where device is available) to assess the presence or absence of oesophageal varix/varices. If an endoscopy has been done within 12 months of Day 0 and a report/adequate data are available, a pretreatment endoscopy at Day 0 is not required. If the endoscopy cannot be performed on Day 0 (eg, device/technician unavailability, scheduling issues, etc), the procedure may be completed within the screening visit window, as close as possible to the Day 0 visit, preferably, after subject eligibility has been confirmed.
 - Subsequent endoscopies should be performed annually or per standard of care and the Investigator's clinical judgment throughout the course of the study.
Endoscopies should also be performed when platelet counts are $<150 \times 10^9/L$.
- Assess and record any pretreatment-emergent AEs.

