11.1.2. Secondary Assessments

The following secondary efficacy assessments will be measured:

- Liver-related death
- Liver biochemistry (see [Table 10](#) for list of analytes to be tested)
- Progression to cirrhosis as assessed by the presence of clinical, laboratory, or radiological evidence of cirrhosis and/or liver stiffness (Fibroscan® TE), confirmed by biopsy unless not medically indicated.
- Histological assessment of disease progression or improvement using paired biopsies in a subset of subjects (see [Appendix C](#))
- Biomarkers, including other markers of hepatic fibrosis and/or inflammation, to be tested will include: IgM, c-reactive protein (CRP), tumor necrosis factor- α (TNF- α), FGF-19, cytokeratin-18 (CK-18) and ELF, (and others as determined during the course of the study).
- Data will be collected to inform quality of life and cost-effectiveness analyses that are relevant to major health care systems around the world. Quality of life will be assessed by questionnaires (PBC-40, EQ-5D-5L, and FIS) administered annually. Resource utilization information will be collected from the Medical and Surgical Treatment Procedures and Office Visit Log or other CRFs such as number, type and duration of hospitalizations, number of outpatient physician visits (subject reported), and use of concomitant medications.
- Endoscopy will be conducted at selected study sites where the device is available to assess for the presence of oesophageal varix/varices at baseline. Throughout the study, any endoscopy performed as part of the annual study assessments or standard of care will be collected in the case report form to assess for the development of varix/varices.

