13.1. Efficacy Analysis

13.1.1. Analysis Populations

The following subject populations will be evaluated and used for presentation and analysis of the data:

- The Intent-to-Treat (ITT) Population will include all randomized subjects who receive any amount of investigational product (OCA or placebo). The ITT Population will be the primary population used for efficacy analyses. Treatment assignment will be based on the randomized treatment.
- The Safety Population will include all subjects who received any amount of investigational product (placebo or OCA). The Safety Population will be the primary population used for safety analyses. Treatment assignment will be based on the treatment actually received.
- The PK population will include all OCA subjects who have at least one confirmed fasted analyzable sample. Subjects must have been fasting for approximately 8 hours prior to the visit and must not have any major protocol deviations that potentially affect exposure levels. The PK population will be used for OCA PK analyses.
- The Overall Historical Control Population will include subjects from the United Kingdom (UK) -PBC Group and Global PBC Study Group databases with demonstrated comparability to randomized subjects in this clinical study (747-302) with respect to both subject characteristics and disease progression.
- The UK-PBC Historical Control Population will include subjects from the UK-PBC Group databases with demonstrated comparability to randomized subjects in this clinical study (747-302) with respect to both subject characteristics and disease progression.
- The Global PBC Historical Control Population will include subjects from the Global PBC Study Group database with demonstrated comparability to randomized subjects in this clinical study (747-302) with respect to both subject characteristics and disease progression.

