The primary efficacy analysis will compare OCA to placebo with respect to the primary efficacy endpoint using the ITT population. The 2 treatment groups will be compared using the log rank test stratified by the randomization stratification factor. Kaplan Meier (KM) estimates of the distribution of the time-to-event will be tabulated and graphed by treatment group. The tabulation will include the KM estimate of the medians and corresponding 95% confidence intervals (CIs), if the medians can be estimated. The number and percent of subjects censored and with events will be presented. The hazard ratio and its 95% CI will be determined based on a Cox regression model stratified by randomization strata to estimate the magnitude of the effect. The same analyses for primary efficacy endpoints will be performed for PP population as a sensitivity analysis.

Key Secondary Efficacy Analyses

The key secondary efficacy endpoints are as follows:

- Time to first occurrence of MELD score ≥ 15
- Time to liver transplant or death (all-cause)
- Change from Baseline in total bilirubin at end of study
- Change from Baseline in ALP at end of study

The key secondary efficacy analyses will compare OCA to placebo in the ITT population with respect to the key secondary efficacy endpoints. Only adjudicated events will be included in time-to-event analyses. The comparison (hypothesis testing) will be conducted in a sequential closed testing gate-keeping procedure (in the order in which the key secondary endpoints are stated above), provided that the primary efficacy endpoint comparison is statistically significant in favor of the OCA treatment group. If the primary comparison is not statistically significant then comparison of the secondary endpoints will be considered as descriptive and exploratory. The same analyses for key secondary efficacy endpoints will be performed for PP population as a sensitivity analysis.

Additional Secondary Efficacy Analyses

The following time-to-event secondary efficacy analyses will compare OCA versus placebo using the ITT population:

- Time to each component of the primary efficacy endpoint (except MELD score ≥ 15 which is captured above)

- Time to development of varix/varices
- Progression to cirrhosis
- Time to occurrence of HCC
- Time to liver-related death
- Time to liver-related death or liver transplant
- Time to liver-related death, liver transplant, or MELD score ≥ 15

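### Time to development of varices is fixed in the ITT population, with no varix-free baseline condition and with censoring at last contact rather than last endoscopy

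*Protocol*

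**What the plan says.** The document at hand holds the body of Protocol Version 3.1, followed by the opening sections of Version 4.

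- **Population and method.** Section 13.1.5 (Version 3.1) introduces its list with "The following time to event secondary efficacy analyses will compare randomized OCA versus randomized placebo using the ITT population". One item is "Time to development of varix/varices". The section adds: "The same analysis methodology as used for the primary efficacy analysis will be used for these secondary efficacy analyses". Section 13.1.1 defines ITT as everyone randomized who took any study drug, with no condition on baseline varices or on having had an endoscopy.
- **Version 4.** The synopsis keeps the endpoint under "The following time-to-event secondary efficacy analyses will compare OCA versus placebo using the ITT population".
- **Censoring.** Section 13.1.9.1 censors subjects without an event at last contact.
- **Eligibility.** Section 8.3 excludes a variceal bleed (present, or within the past 12 months) but not varices as such. Section 9.7.3.1 lists varices among the cirrhosis indicators assessed at Screening Visit 1.
- **Baseline endoscopy.** Section 11.1.2 says: "Endoscopy will be conducted at selected study sites where the device is available to assess for the presence of oesophageal varix/varices at baseline". Section 9.7.7 asks for it on Day 0 where a site has the device, and accepts a report up to 12 months old.
- **On-study endoscopy.** Section 9.7.7 makes it annual or per standard of care, and adds "Endoscopies should also be performed when platelet counts are" below 150 × 10⁹/L. The Table 2 footnote in Section 7.1.2 says: "Endoscopy will be conducted at all study sites where the device is available". Section 11.1.2 collects any annual or standard-of-care endoscopy.
- **The parallel endpoint.** Section 13.1.5 and the Version 4 synopsis both assess progression to cirrhosis only in subjects judged non-cirrhotic at baseline.

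**The concern.** Time to development of a condition has meaning only for subjects known to be free of it at time zero and examined for it afterwards. The stated population guarantees neither. Some ITT subjects may already have varices, some will have no baseline endoscopy, and some may never be scoped.

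Two things are at stake. Varices that predate randomization cannot have been prevented by treatment, so counting them pulls the hazard ratio toward 1. Subjects who are never examined add event-free time without information, so the Kaplan-Meier curve estimates neither incidence nor prevalence. Detection also follows severity, because low platelets and standard of care prompt endoscopy.

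**Working it through.** **1. The plan's own figures.** None is given for this endpoint. The 127 events and 428 subjects belong to the primary composite, and they reproduce. Freedman's formula at a hazard ratio of 0.60 gives 126 events. Event probabilities of 0.398 and 0.263 average 0.331, so 127 / 0.331 ≈ 384 subjects, and 384 / 0.90 ≈ 427 with the 10% dropout stated in Version 4. Nothing below depends on this, except that 0.60 is borrowed as an illustrative effect.

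**2. What the written rules do with each kind of ITT subject.**

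| Baseline endoscopy | On-study endoscopy | Treatment under 13.1.5 and 13.1.9.1 |
|---|---|---|
| Done, no varices | Done | Valid: truly at risk and examined |
| Done, no varices | None | Event-free to last contact, unexamined |
| Done, varices present | Any | In the risk set although development is impossible; no rule on counting |
| Not done | Done, varices found | Can count as new; onset cannot be established |
| Not done | None | Event-free to last contact, status never known |

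Only the first row supports the endpoint.

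**3. Illustrative size by a simple mixture.** Let p be the share of the analysed set whose pre-existing varices are counted as on-study events, and q the placebo incidence among those truly at risk. Neither is in the documents. The pre-existing share of placebo events is s = p / (p + q(1 − p)). The observed hazard ratio is roughly 0.60(1 − s) + 1.00s = 0.60 + 0.40s.

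| p | s (q = 0.15) | HR (q = 0.15) | s (q = 0.30) | HR (q = 0.30) |
|---|---|---|---|---|
| 0.05 | 0.05/0.1925 = 0.26 | 0.70 | 0.05/0.335 = 0.15 | 0.66 |
| 0.15 | 0.15/0.2775 = 0.54 | 0.82 | 0.15/0.405 = 0.37 | 0.75 |
| 0.20 | 0.20/0.320 = 0.63 | 0.85 | 0.20/0.440 = 0.45 | 0.78 |

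**4. Check by Cox simulation.** Assumptions: placebo incidence 4% per year, true hazard ratio 0.60, follow-up 6 to 10 years, and 50% or 75% of subjects scoped yearly. Every pre-existing varix in a scoped subject is counted at the first annual endoscopy, so this is a high case for miscounting.

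| Baseline prevalence | HR, all ITT | HR, scoped and varix-free at baseline | Pre-existing share of counted events |
|---|---|---|---|
| 10% | 0.73–0.74 | 0.59–0.60 | 34–35% |
| 20% | 0.79–0.81 | 0.59–0.60 | 54–55% |
| 30% | 0.84–0.85 | 0.59–0.60 | 67% |

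The rate can err either way. At 10% prevalence and 50% scoping, the placebo event proportion is 0.166 in ITT against 0.258 in the at-risk set. At 30% and 75% it is 0.362 against 0.259.

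**The case against.** **A reader might infer that varices known at baseline are counted as new events.** No passage says so. Section 11.1.2 separates presence at baseline from later development, and on that wording a varix seen on Day 0 has not developed on study. What stands is narrower: such subjects have no stated rule and remain in the risk set. Miscounting follows most directly for subjects with no baseline endoscopy.

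**Adjudication may filter events.** Section 13.1.9.1 admits only adjudicated events, so a committee could reject a documented pre-existing varix. It cannot supply a missing baseline endoscopy. The outcome list in Section 12.1.5 names variceal bleeding but not varices.

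**At-risk flags are usually left to the SAP.** That is fair for derivation detail. Here, however, the protocol names the population, and it writes a baseline-free restriction for progression to cirrhosis but none for varices. The Version 4 synopsis lists both under one ITT header and restricts only cirrhosis. The header therefore does not preclude a subset, but none is stated for varices.

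**Most of the cited text is Version 3.1.** This is correct. Of Version 4, only the synopsis reaches this endpoint in the pages shown. It confirms the ITT population, but the Version 4 text on endoscopy and censoring cannot be seen. For that reason little should be made of the different wording on selected and all sites. Both wordings limit endoscopy to sites with the device, and the argument does not need the difference.

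**A reader might infer a bias in favor of OCA.** The documents do not support this. Randomization balances pre-existing varices and missing endoscopies in expectation, so the main effect is dilution. Severity-driven scoping could make detection differ by arm, but nothing shown establishes that it does.

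**Conclusion.** The point holds as a poorly fixed analysis population and censoring rule for an onset endpoint. Three defects follow from the text: possible counting of varices of unknown onset, unexamined subjects carried as varix-free to last contact, and subjects with known varices kept at risk.

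The expected result is dilution toward 1 and a rate that cannot be read as incidence. The move from 0.60 to about 0.70–0.85 is illustrative only. It rests on assumed prevalence and incidence and on pre-existing varices being counted; with 30% incidence the same formula gives 0.66–0.78. If few subjects lack a baseline endoscopy and known varices are rejected, the effect on the hazard ratio would be smaller.

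The consequence is limited. Section 13.1.10 places this endpoint outside the gate-keeping sequence and makes its test descriptive and exploratory. The primary and key secondary analyses are unaffected. It should be corrected because the correction is simple, not because a main conclusion is at risk.

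**What to change.** In the synopsis and Section 13.1.5, for this endpoint only:

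1. Restrict the analysis to ITT subjects with a varix-free endoscopy on Day 0 or within the 12 months that Section 9.7.7 already accepts, parallel to the restriction for progression to cirrhosis. This is a pre-treatment characteristic, so the randomized comparison within the subset is preserved.
2. Count as the event the first later endoscopy that shows varices.
3. Censor event-free subjects at their last endoscopy, not at last contact. Without this, a subject with a clean baseline and no later endoscopy would still count as varix-free.
4. Report by arm the numbers with baseline varices and with no baseline endoscopy, and the on-study scoping rate, so that any difference in detection is visible.

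This changes wording and analysis only and adds no procedure. The cost is a smaller denominator and a wider interval. How much smaller cannot be said, because the share of subjects with a baseline endoscopy is not given. In the simulation above, about 32 to 61 truly incident events per 428 subjects remained, out of 62 to 144 counted in ITT. Severity-driven scoping is not removed by these changes; item 4 only makes it visible.

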9.7.3. Assessing Cirrhosis

9.7.3.1. Determination for Dosing Regimen

To determine which dosing regimen subjects should follow, the presence or absence of cirrhosis should be assessed by the Investigator at Screening Visit 1. Acceptable methods of confirming (via medical history) or assessing cirrhosis for purposes of determining dosing is defined as a subject who has documented evidence or presence of one or more of the following cirrhosis indicators:

- Biopsy results consistent with PBC Stage 4 ([Ludwig 1978](#))
- Transient Elastography (TE) Median Value ≥ 16.9 kPa ([Corpechot 2012](#))
- The presence of any of the following (unless exclusionary per [Section 8.3](#)) in the absence of acute liver failure:
 - Varices
 - Ascites
 - Radiological evidence of cirrhosis (nodular liver or enlargement of portal vein and splenomegaly)
- Combined low platelet count ($<140\,000/\text{mm}^3$) with:
 - persistent decrease in serum albumin, or
 - elevation in prothrombin time /INR (not due to antithrombotic agent use), or
 - elevated bilirubin ($2\times$ ULN)

Subjects who exhibit no evidence of cirrhosis by the above methods of assessment will be dosed using the Standard Dosing Regimen, while those who do exhibit evidence of cirrhosis by one or more of the above methods will be dosed using the Modified Dosing Regimen according to their Child-Pugh Score calculated in the electronic case report form (eCRF) (see [Appendix A](#), [Section 7.3](#), [Table 3](#) and [Table 4](#)).

Cirrhosis status should be reassessed as clinically indicated throughout the study. Any change in cirrhosis status will necessitate re-evaluation of the dosing regimen.

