9.7.3.2. Progression to Cirrhosis

When a subject identified as non-cirrhotic at baseline per the criteria listed in [Section 9.7.3.1](#) exhibits any of those same criteria (excluding biopsy results consistent with PBC Stage 4), the subject should also be assessed by Fibroscan® TE where available and progression to cirrhosis confirmed by biopsy unless not medically indicated. Sites participating in the paired biopsy sub-study (see [Appendix C](#)) must confirm progression to cirrhosis by biopsy. All suspected cases of progression to cirrhosis should be submitted for adjudication regardless of the availability of transient elastography or biopsy results.

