The same analysis methodology as used for the primary efficacy analysis will be used for these secondary efficacy analyses. Similar endpoints, where available, will be analyzed to compare OCA to historical controls.

Progression to cirrhosis will be assessed in the subset of subjects considered noncirrhotic at Baseline using available medical history, clinical, and laboratory assessments as well as Baseline TE where available. Specifically, subjects with no clinical, laboratory, or radiological evidence of cirrhosis at Baseline and/or a TE liver stiffness of < 16.9 kPa (Corpechot 2012) will be considered noncirrhotic. Progression to cirrhosis will be assessed by the development of clinical, laboratory, or radiological evidence of cirrhosis and/or when liver stiffness increases to ≥ 16.9 kPa during the study in which case histological progression to cirrhosis should be confirmed by biopsy unless not medically indicated. Using this definition for progression to cirrhosis, the percentage of noncirrhotic subjects progressing to cirrhosis during the treatment period will be summarized by treatment group and compared using a Cochran–Mantel–Haenszel test stratified by the randomization stratification factor.

For those subjects enrolled in the biopsy substudy (defined in Addendum 2) progression to cirrhosis identified by the above criteria and improvement in fibrosis/cirrhosis will be confirmed by paired biopsy. Analyses for the histological assessment conducted as part of the biopsy substudy are defined in Addendum 2.

Further details on efficacy, health outcomes, and PK analyses are specified in [Section 13](#).

Safety Analyses

Safety data, including AEs, vitals, electrocardiogram, and clinical laboratory results will be summarized by treatment group for the Safety Population.

Sample Size Justification

The target population is subjects who are at higher risk of liver-related clinical complications. Eligible subjects will have a diagnosis of PBC with bilirubin levels $> \text{ULN}$ and $\leq 5x \text{ ULN}$ and/or ALP $> 3x \text{ ULN}$. The following assumptions were used in sample size calculations:

- Exponential survival curves, placebo survival estimate of 0.6 at 8 years with a hazard ratio of 0.60, and total study duration of 10 years (from first subject enrolled), allowing for 4 years of subject accrual and 6 years of follow-up
- Subjects will be randomized in a 1:1 ratio to placebo or OCA.

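### The baseline rule for progression to cirrhosis contradicts the protocol's own cirrhosis definition, and the Version 4 synopsis gives the endpoint two methods, one open to exposure bias

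*Protocol*

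**What the plan says.** The document holds the body of protocol Version 3.1, then the synopsis and opening sections of Version 4. Version 4's Section 13 is not shown.

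**Baseline risk set.** Version 3.1 Section 13.1.5 defines non-cirrhotic as "subjects with no clinical, laboratory, or radiological evidence of cirrhosis at baseline and/or a TE liver stiffness of" less than 16.9 kPa (transient elastography, TE), with a pointer to Section 9.7.3.1. That section treats as cirrhotic "a subject who has documented evidence or presence of one or more of the following cirrhosis indicators". The indicators are Stage 4 biopsy, TE of 16.9 kPa or more, varices, ascites, radiological evidence, or low platelets with a further laboratory sign. Section 9.7.3.2 starts the progression work-up from the same list: "When a subject identified as non-cirrhotic at baseline per the criteria listed in" Section 9.7.3.1. The Version 4 synopsis keeps the and/or wording: "subjects with no clinical, laboratory, or radiological evidence of cirrhosis at Baseline and/or a TE liver stiffness of" less than 16.9 kPa.

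**Analysis.** In Version 3.1 Section 13.1.5, progression is not in the time-to-event list. Its only stated method is a stratified CMH test in which "the percentage of non-cirrhotic subjects progressing to cirrhosis during the treatment period will be summarized by treatment group".

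The Version 4 synopsis adds progression to a list headed "The following time-to-event secondary efficacy analyses will compare OCA versus placebo using the ITT population" and says of that list: "The same analysis methodology as used for the primary efficacy analysis will be used for these secondary efficacy analyses". It then prescribes the same CMH percentage in the non-cirrhotic subset.

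**The concern.** One endpoint has two incompatible definitions of who is at risk. A programmer following Section 13.1.5 and one following Section 9.7.3.2 would build different analysis sets. Subjects who already have cirrhosis cannot progress to it. They either add events that treatment cannot prevent or sit in the denominator and dilute the difference.

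The second issue is the outcome measure. Planned follow-up runs from 6 to 10 years, and subjects who stop study drug stay on the regular visit schedule (Sections 7.4.2 and 8.4.3). A percentage confined to time on drug would discard cirrhosis found after stopping, and the arm that stops earlier would appear to progress less. The protocol itself gives reasons why time on drug may differ: pruritus as the main OCA-related adverse event (Section 5.6), stopping study drug on starting commercial OCA (Sections 8.4.3 and 9.2.1), and stopping after transplant (Section 8.4.1.2). The percentage-endpoint rule in Section 13.1.9.1 covers only subjects with no data at all after randomization.

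At stake is a secondary endpoint that Version 3.1 added to help relate non-invasive markers to disease progression.

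**Working it through.** **1. The plan's own figures.** The main study states no figure for this endpoint. The primary design figures reproduce: 127 events give 79.7% (Freedman) to 81.3% (Schoenfeld) power with the two interim looks. The mean event probability of 0.331 gives 127/0.331 = 384 subjects, and 384/0.9 = 427, against 428 stated. The only progression rates are in the biopsy sub-study (Appendix C): OCA 0.23 with a 50% risk reduction, hence placebo 0.46. With 22.5 per arm and one-sided alpha 0.2, power is 79.0% against 80% stated. None of these is in doubt.

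**2. The two baseline rules side by side.**

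| Subject at baseline | Section 13.1.5, either condition enough | Sections 9.7.3.1 and 9.7.3.2 |
|---|---|---|
| Varices, TE 12 kPa | Non-cirrhotic | Cirrhotic |
| TE 20 kPa, no other sign | Non-cirrhotic | Cirrhotic |
| Varices, TE not measured | Meets neither condition | Cirrhotic |
| No indicator, TE below 16.9 kPa | Non-cirrhotic | Non-cirrhotic |

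Section 13.1.5 also does not name Stage 4 biopsy, although its mention of medical history may be meant to cover it.

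**3. Effect of prevalent cases.** Take the sub-study rates (0.46 and 0.23) as true, and let an assumed share m of the risk set be already cirrhotic.

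- If all of them count as progressing, each arm's rate is p(1 − m) + m. At m = 10%: 0.46 × 0.9 + 0.1 = 0.514 and 0.23 × 0.9 + 0.1 = 0.307, so the relative risk moves from 0.50 to 0.60. At m = 20% it is 0.384/0.568 = 0.68.
- If none count, each rate is p(1 − m). The relative risk stays 0.50.
- Either way the risk difference is 0.23(1 − m): 0.207 at 10% and 0.161 at 30%.

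**4. Effect of a percentage confined to time on drug.** Let r be the progression hazard, equal in both arms (no true effect), d the yearly discontinuation hazard and T the follow-up. The proportion progressing on drug is

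P = r/(r + d) × (1 − exp(−(r + d)T)).

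With assumed r = 0.05 and T = 8:

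- d = 0.03: 0.625 × 0.473 = 0.295
- d = 0.05: 0.500 × 0.551 = 0.275
- d = 0.10: 0.333 × 0.699 = 0.233

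| Discontinuation, placebo v OCA | False relative risk | Reversed |
|---|---|---|
| Equal | 1.00 | 1.00 |
| 5% v 10% per year | 0.233/0.275 = 0.85 | 1.18 |
| 3% v 10% per year | 0.233/0.295 = 0.79 | 1.27 |

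A second version uses the sub-study's placebo risk of 0.46, placed by assumption over 8 years (hazard −ln(0.54)/8 = 0.077), and averages over follow-up of 6 to 10 years. It gives 0.85 and 1.18 for the first pair, and 0.80 and 1.26 for the second. With an assumed 150 subjects per arm, a two-sided 5% test then rejects 18% and 33% of the time with no true effect. Under equal discontinuation it rejects 5% of the time.

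**The case against.** The and/or wording is probably a drafting slip. Section 13.1.5 mentions TE where available and points to Section 9.7.3.1, so the authors may only have meant to allow for sites without the device. That is plausible, but the sentence still contradicts the section it cites, and Version 4 carries it forward.

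A reader might infer that prevalent cases automatically become progressions at their first visit. The text does not support that: it requires cirrhosis evidence to develop or stiffness to rise to the threshold, it expects biopsy confirmation unless not medically indicated, and suspected cases go to adjudication. Section 13.1.5 does not say how those words apply to someone already past the threshold, which is why step 3 shows both outcomes. The extra admissions also need a TE measurement, so they arise only where one was made.

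A reader might also infer that Version 3.1 Section 13.1.5 contradicts itself on method. It does not, since CMH is its only stated method. The conflict is within the Version 4 synopsis, and Version 4's Section 13, which might resolve it, is not at hand. The Kaplan–Meier analysis in Appendix C belongs to the sub-study and is no conflict.

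Finally, the treatment period is not defined in the text shown, and Section 13.1.5 also speaks of stiffness rising during the trial. Randomization balances calendar follow-up. Bias therefore needs both the on-drug reading and a difference between arms in discontinuation, death or transplant, and the documents give no such rates.

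**Conclusion.** Two points stand on the text alone. The baseline rule in Section 13.1.5, repeated in the Version 4 synopsis, contradicts Sections 9.7.3.1 and 9.7.3.2 when read literally. The Version 4 synopsis also assigns two methods to one endpoint.

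The third is conditional. If the treatment period means time on study drug, the CMH percentage is biased when time on drug differs by arm. The false relative risk is 0.79 to 1.27 over the assumed discontinuation rates, in either direction, and there is no bias when the arms stop equally. A reader might infer a bias in favour of OCA, but the documents do not fix the direction: intolerance would shorten OCA exposure, while switching to commercial OCA could shorten either arm's. The share of prevalent cases and the discontinuation rates are assumptions.

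Progression to cirrhosis lies outside the testing sequence of Section 13.1.10, so confirmatory type I error is unaffected. The change should be made, but no confirmatory claim depends on it.

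**What to change.** - **Baseline definition.** State in Section 13.1.5 and the synopsis that non-cirrhotic means having none of the Section 9.7.3.1 indicators, including Stage 4 biopsy, with TE below 16.9 kPa where TE was measured. This concerns the analysis set only and leaves the dosing determination as it is.
- **Main analysis.** Use time from randomization to adjudicated progression, by stratified log-rank test and cause-specific Cox model, over all study follow-up regardless of study drug discontinuation. Handle death and transplant in the same way, as competing events, for example with cumulative incidence curves.
- **CMH percentage.** Keep it at most as a descriptive summary, with the treatment period defined.

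The cost is wording in the protocol and SAP; no visits or data are added. The risk set becomes slightly smaller. Counting follow-up after stopping drug will include any placebo subjects who start commercial OCA, which may dilute a true effect.
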